The primary outcome measure is the blind assessor-rated Y-BOCS, which will be administered at pre-treatment, at weeks 4 and 7 during treatment, 14 weeks after treatment start (primary endpoint), and at the 7- and 16-month follow-ups [21]. Blinded assessors will undergo training prior to conducting clinician-rated assessment and practice on videos of OCD case examples. In order to be allowed to conduct assessments for the project, the assessors will have to deviate no more than 1 point on single items, no more than 2 points on the obsessions subscale and the compulsions subscale and no more than 4 points on the Y-BOCS total score compared to expert raters at the two clinics. Inter-rater reliability on the Y-BOCS will be reported.

Secondary clinician-administered outcome measures are the Clinical Global Impression – Severity and Improvement (CGI-S, CGI-I), the Patient Exposure/Response Prevention Adherence Scale (PEAS), the Structured Clinical Interview for DSM-5 for OCD and related disorders (SCID-5) and the Mini International Neuropsychiatric Interview. SCID-5 and MINI will be administered at pre-treatment to confirm the OCD-diagnosis and assess comorbidities

Secondary self-rated outcome measures are the Obsessive-Compulsive Inventory-Revised (OCI-R), self-rated Y-BOCS, Montgomery-Åsberg Depression Rating Scale—Self-Rated (MADRS-S), Work and Social Adjustment Scale (WSAS), Assessing Quality of Life 6 Dimensions (AQoL-6D) (for economic evaluation), Credibility/Expectancy Questionnaire (CEQ), Working Alliance Inventory—Short Form Revised (WAI-SR), the TIC-P resource use questionnaire (for economic evaluation), and the Negative Effects Questionnaire (NEQ). Participants will also rate their treatment preference measured on a 7-point Likert-type scale (pre-treatment and post-treatment).

Table 2. Assessments of secondary outcomes at different time points

	Pre-treatment	Week 4	Week 7	Week 15 (primary end-point)	7-month follow-up	16-month follow-up
Clinician-rated instruments						
SCID-5 (OCD)	X					
MINI	X					
Y-BOCS	X	X	X	X	X	X

CGI-S	X	X	X	X	X	X
CGI-I		X	X	X	X	X
PEAS*		X	X	x		
Self-rated instruments						
YBOCS-SR	X			X	X	X
OCI-R	X			X	X	X
MADRS-S	X			X	X	X
WSAS	X			X	X	X
AQoL-6D	X			X	X	X
TIC-P	X			X	X	X
NEQ				X	X	X
Other adverse events		X	X	X	X	X
CEQ**		X				
WAI-SR**		X				
Treatment preference	X			X		

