Although there are no strict guidelines regarding the selection of non-inferiority margins, half the placebo-controlled effect of gold-standard treatment is often recommended as adequate [23]. The proposed non-inferiority margin of 4 is smaller than half of the 10-point effect for ERP on the Y-BOCS [4], and would therefore be a stringent non-inferiority margin. Moreover, a non-inferiority margin of 4 points gives similar precision compared to previous non-inferiority trials for OCD in adults that have used 5 points [19] or 3 points [20], and a previous non-inferiority trial in pediatric OCD that used a margin of 4 points [30]. From a clinical point of view, a 4-point margin on the Y-BOCS is considered a small but observable difference in OCD symptoms.

Secondary outcomes

While this study was designed to have high power to assess the primary hypothesis, we do not have sufficient power to robustly compare the secondary outcomes between the treatment arms without inflating the false positive rate. This means that the results from these analyses should be interpreted with caution. On secondary outcomes, our approach will be to compute 95% confidence intervals of group differences without comparing the bounds to any predefined margin. Because the non-inferiority testing procedure will not apply, the secondary outcomes will be analyzed using an intent to treat approach including all randomized participants.

Moreover, we do not plan to collect data continuously throughout the treatments since our focus is on the pre-post comparisons. This decreases the usefulness of statistical methods that make imputations based on past observations. Therefore, unless the proportion of missing data exceeds 10%, no data imputation methods will be used as default (unless stated otherwise). However, if the proportion of missing data exceeds 10%, we will perform maximum likelihood imputations based on demographics and the scores from the pre-treatment assessment to complement the complete case analyses. The implications of these analyses on the reliability of the results will be discussed.

Time to response

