(pretreatment) or the past 14 weeks (post-treatment and follow-up), and costs will be extrapolated to cover the entire period between assessments when needed. Costs from third party payer (including only intervention costs), healthcare, and societal perspectives will be analyzed in relation to clinical efficacy (responder status; cost-effectiveness analysis) and quality-adjusted life-years on the AQoL-6D (QALYs; cost utility analysis). Additional cost-effectiveness analyses will use remitter status as outcome. The economic analysis will be conducted using multiple imputation of missing values. Cost data and QALYs will be analyzed using generalized linear models (GLM) to allow for the consideration of other distributions and functional forms to fit the cost and outcome data [24]. Total costs will be analyzed while controlling for baseline costs. Total QALYs will be analyzed while controlling for baseline AQoL-6D utility values [25].

A micro costing framework will be used to estimate the cost of delivering the interventions prospectively. Intervention costs will include the therapists' time to deliver sessions, as well as any training needed. Healthcare resource use will be costed using national pricelists, and medication costs using market prices, and estimated by multiplying frequencies of resources used by unit costs. Unit costs for resources related to social support and assistance will be sourced from published sources or based on authors' own estimates. Productivity losses will be estimated using the human capital approach [26]. Productivity losses due to absenteeism from paid work will be the product of the number of days off from work by individuals due to mental illness by the average hourly salary rate in Sweden [27] including social fees. Losses due to absenteeism from unpaid work will be the product of the number of days not performing unpaid work by the estimated hourly cost of leisure time [28]. Productivity losses related to reduced efficiency at work will be estimated in the same fashion as productivity losses due to absenteeism, but additionally multiplied by a weighed score representing how the illness impacted the participants' productivity [29].

Additional outcomes used for quality assessment

Therapist competence and adherence

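### Week-14 response and remission are called intent-to-treat but default to complete cases up to 10% missing, and the fallback imputation leaves out the week 4 and 7 ratings

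*Combined protocol and SAP*

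**What the plan says.** Under Statistical analysis, Secondary outcomes, the combined protocol and SAP states that "the secondary outcomes will be analyzed using an intent to treat approach including all randomized participants". The next paragraph then sets the missing-data rule: "unless the proportion of missing data exceeds 10%, no data imputation methods will be used as default", with room for exceptions stated elsewhere. Above 10%, the plan adds "maximum likelihood imputations based on demographics and the scores from the pre-treatment assessment to complement the complete case analyses". The reason given is that "we do not plan to collect data continuously throughout the treatments since our focus is on the pre-post comparisons", which is said to make imputation from past observations less useful.

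The Measurements section schedules the blind-rated Y-BOCS "at pre-treatment, at weeks 4 and 7 during treatment", then at 14 weeks and at both follow-ups. Table 2 lists CGI-S and CGI-I at weeks 4 and 7 too. Response needs a Y-BOCS reduction of at least 35% and a CGI-I of 1 or 2. Remission needs a Y-BOCS of 12 or less and a CGI-S of 1 or 2. Under Rates of response and remission, both are compared with a two-sided two-proportion z-test, and nothing is said about a patient with no week-14 rating.

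The Cost effectiveness section is an exception: "The economic analysis will be conducted using multiple imputation of missing values". Responder status is the effect measure in its cost-effectiveness analysis.

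**The concern.** The named analysis set and the missing-data rule do not agree. At or below 10% missing, a patient without a week-14 rating leaves the response and remission analyses, so the set is no longer everyone randomised. Above 10%, the complete-case result stays and the imputed result stands beside it.

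The reason given does not fit these two outcomes. All their components are rated twice between baseline and week 14, and the plan itself analyses responder status at weeks 4 and 7. A recent rating of the same construct is usually the best available predictor of a missing one, and the rule leaves it out.

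The conditions for bias are ones the document itself considers possible. The Introduction says the length of standard CBT raises the risk of dropout. Limitations raises dropout caused by travel distance. The primary Y-BOCS analysis gets an intention-to-treat sensitivity analysis aimed at non-random missing data, but response and remission get no counterpart at or below 10%. At stake are the response and remission rates and their difference between arms. The report could also carry one week-14 response rate in the clinical results and another in the economic results.

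**Working it through.** **1. The plan's own figure.** The only computed design figure is power above 95% for the primary test. Inputs from Sample size calculation: 60 per arm, 10% missing, post-treatment SD 4.07, margin 4, no true difference. The one-sided alpha of 0.025 comes from the primary analysis section. Ignoring the baseline covariate:

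- patients per arm: 60 × 0.90 = 54
- SE = 4.07 × √(2/54) = 0.783
- power = Φ(4/0.783 − 1.96) = Φ(3.15) = 99.9%

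Simulated ANCOVAs (10,000 datasets) gave 99.9% with no pre-post correlation and 99.99% with a correlation of 0.5. The stated power is reproduced and not in dispute. What matters here is the planned 10% missing: 12/120 = 10% does not exceed the trigger. The text does not say whether the 10% is counted overall, per arm or per outcome.

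**2. Complete-case response rate.** Let p be the true response rate, m the share missing in an arm and q the response rate among the missing. The complete-case rate is (p − m·q)/(1 − m). Take p = 65% in both arms: this is the Introduction's figure for CBT, and its use for B4DT is an assumption. With 12 of 120 missing:

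| Missing B4DT / CBT | q (assumed) | B4DT | CBT | Difference, points |
|---|---|---|---|---|
| 10% / 10% | 0 | 0.65/0.90 = 72.2% | 72.2% | 0.0 |
| 5% / 15% | 0 | 0.65/0.95 = 68.4% | 0.65/0.85 = 76.5% | −8.0 |
| 5% / 15% | 25% | 0.6375/0.95 = 67.1% | 0.6125/0.85 = 72.1% | −5.0 |
| 5% / 15% | 65% | 65.0% | 65.0% | 0.0 |

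Reversing the split reverses the sign. In simulation, the z-test at the 5% level rejects in about 15% of trials in the second row and about 9% in the third.

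**3. Missingness that depends on the week-7 score.** A large-sample simulation of the Y-BOCS part of response had a true rate of about 68% in both arms. The between-visit correlations, week 4 and 7 means and dropout model are assumptions, because the documents give none. The stronger dependence has twice the slope of the weaker. Bias in B4DT minus CBT, in points:

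| Missing B4DT / CBT | Dependence | Complete case | Baseline-only imputation | Imputation with weeks 4 and 7 |
|---|---|---|---|---|
| 5% / 15% | weaker | −1.5 | −1.8 | 0.0 |
| 5% / 15% | stronger | −2.2 | −2.8 | −0.1 |
| 2% / 18% | weaker | −2.4 | −2.9 | 0.0 |
| 2% / 18% | stronger | −3.5 | −4.4 | +0.1 |
| 5% / 25% (15% overall, trigger met) | stronger | −4.1 | −5.2 | 0.0 |

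With 10% / 10% missing the difference is unbiased. Under the stronger dependence, each arm's complete-case rate is about 2.6 points too high. In this model the planned fallback does not remove the bias and slightly enlarges it. Imputation with weeks 4 and 7 removes it because missingness was made to depend on the week-7 score.

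**4. Scale.** The 95% CI half-width for the difference with 60 per arm is 1.96 × √(2 × 0.65 × 0.35/60) = 17.1 points.

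**The case against.** The strongest reply is that these outcomes are declared exploratory and underpowered, and that a bias of a few points is small beside a half-width of 17 points. In context, intent-to-treat mainly marks a contrast with the per-protocol primary set. The plan openly calls its default complete case and promises to discuss the implications. Week-14 Y-BOCS already gets an intention-to-treat sensitivity analysis by maximum likelihood. All of this stands and limits the weight of the point. It does not answer it, because exploratory status concerns power and multiplicity, not bias or the analysis set.

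Several stronger readings are tempting but not supported:

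- A reader might infer that the plan denies collecting any data during treatment. It says only that collection is not continuous, and two visits do not contradict that.
- A reader might extend the point to every secondary outcome. Table 2 shows no self-rated symptom scale, and no NEQ, at weeks 4 or 7. The dropout outcome rests on attendance, and the economic analysis is already multiply imputed.
- A reader might equate treatment dropouts with missing ratings. A patient who attends less than half of treatment can still be rated at week 14. The documents give no data linking missing ratings to outcome.
- A reader might take the extreme case as the expected size. With all 12 missing patients in one arm and all non-responders, 39/60 = 65% would show as 39/48 = 81%. That also needs the 10% to be counted overall, which the text does not settle.

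The analysis scripts are in a public repository that was not available here, and they may give more detail.

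**Conclusion.** The point holds for week-14 response and remission. The plan names an all-randomised analysis but specifies complete cases at or below 10% missing. Its fallback leaves out ratings of the same components that the trial will already hold. Because the economic analysis imputes by another method, two week-14 response rates are possible.

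Bias in the difference between arms requires missingness that relates to outcome, with the amount missing or that relation differing by arm. With 10% missing overall, the size is about 2 to 4 points when missingness depends on the week-7 score, under assumed correlations and an assumed dropout model. It is about 8 points with a 5%/15% split if every missing patient is a non-responder, which is a not-at-random assumption. With equal missingness that relates to outcome in the same way in both arms, only the arm-level rates are inflated. If the missing respond like the rest, there is no bias. The primary non-inferiority test is not affected. This is a cheap improvement to exploratory outcomes and does not threaten the trial's main conclusion.

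**What to change.** For response and remission, remove the 10% trigger. Make the main analysis multiple imputation by arm in all randomised patients. The imputation model should include pre-treatment, week 4 and week 7 Y-BOCS and the CGI ratings available at each visit. Use the same imputed sets in the economic analysis, so that one response rate serves both.

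Keep complete case as a sensitivity analysis. Add one that counts missing as non-response, or a delta-adjusted imputation. This is needed because standard multiple imputation assumes missing at random and would not repair the case where all missing patients are non-responders. Patients lost before week 4 also have no interim rating to borrow from.

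For the self-rated scales and the NEQ, the week 4 and 7 clinician ratings can serve only as auxiliary variables. If a trigger is kept for those outcomes, state whether it is counted per outcome, per arm or overall.

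The cost is SAP wording and slightly more analysis work. No extra data are needed, and multiple imputation is already planned.

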Abbreviations: AQoL-6D, Assessing Quality of Life 6 Dimensions; CEQ, Credibility/Expectancy Questionnaire; CGI-I, Clinical Global Impression–Improvement; CGI-S, Clinical Global Impression–Severity; MADRS-S; Montgomery–Åsberg Depression Rating Scale–Self-Rated; MINI, Mini International Neuropsychiatric Interview; NEQ, Negative Effects Questionnaire; OCI-R, Obsessive–Compulsive Inventory–Revised; PEAS, Patient Exposure/Response Prevention Adherence Scale; SCID-5, Structured Clinical Interview for DSM-5 Disorders; TIC-P, Treatment Inventory of Costs in Psychiatric Patients; WAI-SR, Working Alliance Inventory–Short Form Revised; WSAS, Work and Social Adjustment Scale; Y-BOCS, Yale–Brown Obsessive Compulsive Scale; Y-BOCS-SR, Yale–Brown Obsessive Compulsive Scale–Self-Rated; Other adverse events, semi-structured questions about potential severe adverse events and psychiatric care outside the study

* PEAS rated once at the last day of B4DT treatment

** CEQ and WAI-SR rated by participants at the last day of B4DT treatment and week 2 in individual CBT

Treatment-response will be defined as a $\geq 35\%$ reduction on the Y-BOCS and a Clinical Global Impression–Improvement (CGI-I) score of 1 ("very much improved") or 2 ("much improved"). Remission will be defined as a score of ≤ 12 on the Y-BOCS and a Clinical Global Impression–

Severity (CGI-S) rating of 1 ("normal, not at all ill") or 2 ("borderline mentally ill"). Recovery will be defined as a sustained remission status at the long-term follow-ups[8].

Safety and adverse events

Data on adverse events including suicidal ideation, and initiation of additional psychiatric care, will be collected at each assessment following inclusion, as well as through the regular contact between participants and therapists during treatment. A standardized self-rated questionnaire (Negative effects questionnaire, NEQ; [9]) containing 32 questions about incidents and negative effects will be used at the primary endpoint and follow-ups.

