To explore whether B4DT leads to a faster treatment response than individual CBT, the proportion of responders in the two treatments will be compared 4 weeks after treatment start. The 95% confidence intervals of the odds ratio of response will be calculated for this purpose. Because the B4DT-group will have received their full treatment dose at the point of assessment while the gold standard CBT-group will have received only about 25%, there are strong reasons to believe that, from this perspective, B4DT will lead to faster symptom relief. An identical analysis will be conducted at 7 weeks to evaluate whether there is a difference between the treatments when participants in the individual CBT group have received 50% of the treatment.

Rates of response and remission

The proportion of participants in response and remission will be compared 14 weeks after treatment start. Response is defined as a reduction of 35% or more on the Y-BOCS and a CGI-I score of 1 or 2. Remission is defined as a Y-BOCS score of 12 or less and a CGI-S score of 1 or 2. Proportions will be compared using a two-sided two-proportions z-test.

Dropout rate

To explore whether the groups differ in terms of treatment completion, we will compare whether the proportion of patients that discontinue treatment prematurely differs between B4DT and gold standard CBT. A dropout will be defined as a patient in the B4DT arm that participates in less than 1.5 full days at the clinic, or a patient in the gold standard CBT arm that participates in less than 8 CBT sessions. Proportions will be compared using a two-sided two-proportions z-test.

Negative effects

To describe negative treatment effects, a two-sample t-test will be used to compare the total NEQ-scores at the primary endpoint (scores on the subscales will be presented in the supplement). The additional semi-structured questions about suicidal behaviors and thoughts, hospitalization, deterioration of psychiatric symptoms, and psychiatric care outside the study, will be reported in a frequency table.

Cost effectiveness

Health economic data will be collected using the self-rated Treatment Inventory of Costs in Psychiatric Patients (TIC-P) questionnaire [11]. The TIC-P records costs for the past month

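### The imputation described for secondary outcomes omits randomised arm, so it shrinks true group differences by about the missing share

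*Combined protocol and SAP*

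**What the plan says.** Under Statistical analysis, Secondary outcomes, the plan states that "the secondary outcomes will be analyzed using an intent to treat approach including all randomized participants". Its approach is to "compute 95% confidence intervals of group differences without comparing the bounds to any predefined margin". Nothing is imputed by default unless missing data exceed 10%. Above that level the plan adds "maximum likelihood imputations based on demographics and the scores from the pre-treatment assessment", and it does so "to complement the complete case analyses". What the imputed results imply for reliability is then to be discussed. Arm is not in the list of inputs, and no other section names it as an imputation predictor.

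For the NEQ, the Negative effects section says that "a two-sample t-test will be used to compare the total NEQ-scores at the primary endpoint". According to Safety and adverse events, the questionnaire "will be used at the primary endpoint and follow-ups", and Table 2 shows no pre-treatment NEQ.

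Two secondary outcomes are handled differently. Dropout is defined by attendance, and the economic analysis has its own multiple imputation. The Statistical analysis section also says that the scripts are in a public repository; they were not available for this review.

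**The concern.** All the listed inputs are measured before treatment. Randomisation balances them between arms apart from chance, so they cannot stand in for arm. A model built on them alone predicts missing values in both arms from one common regression, and so it fills both arms with values that lie between the two arm means. The more values are filled in, the closer the arm means move together.

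The imputed analysis exists to show whether the complete-case result can be relied on. If it moves real differences towards zero, a sound complete-case finding looks fragile for an artificial reason. This matters most where a real difference is expected, as with early response at week 4, the one secondary outcome with a directed hypothesis. It also matters for negative effects, where understating a difference is the less safe error.

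**Working it through.** **1. The plan's own figure.** The plan gives no figure for the secondary-outcome imputation. Its one design figure is power above 95% for the primary test (Sample size calculation). With 60 × 0.9 = 54 per arm, SD 4.07, margin 4 and a true difference of 0, the standard error is 4.07 × √(2/54) = 0.783. Then 4/0.783 − 1.96 = 3.15, which gives power of 99.9%. The claim is reproduced, but this point does not depend on it.

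**2. Closed form.** Let mB and mC be the missing shares in the B4DT and CBT arms, with equal arm sizes and values missing at random given baseline. Set the CBT mean to 0 and the B4DT mean to δ.
- Common imputed mean: P = (1 − mB)δ / (2 − mB − mC).
- Difference after imputation: (1 − mB)δ + (mB − mC)P = δ × 2(1 − mB)(1 − mC) / (2 − mB − mC).
- With equal shares m this is δ × (1 − m).
- With 25% and 5% missing: 2 × 0.75 × 0.95 / 1.70 = 0.838.

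**3. Simulation.** 3,000 datasets per setting, 60 per arm, single regression imputation. Assumed, not from the documents: a true difference of 0.5 SD, a baseline-outcome correlation of 0.4, and the missing shares. Entries are the mean estimate divided by the true difference. Where two values are shown, they are without and with a random residual added to the imputed value.

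| Missing, by arm | Formula, no arm | Simulated, no arm | Simulated, with arm | Complete case (range over runs) |
|---|---|---|---|---|
| 10% / 10% | 0.900 | 0.900 / 0.900 | 1.004 / 1.011 | 0.997–1.009 |
| 15% / 15% | 0.850 | 0.850 / 0.841 | 1.004 / 1.005 | 0.992–1.004 |
| 20% / 20% | 0.800 | 0.796 / 0.809 | 1.005 / 0.995 | 0.994–1.016 |
| 30% / 30% | 0.700 | 0.710 / 0.691 | 1.001 / 0.990 | 0.991–1.012 |
| 25% / 5% | 0.838 | 0.835 / 0.832 | 0.995 / 0.994 | 0.994–0.995 |

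A true difference of 0.5 SD would thus appear as about 0.5 × 0.85 = 0.425 SD at 15% missing and 0.5 × 0.70 = 0.35 SD at 30%.

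**4. Interval coverage (nominal 95%).** With arm included but single imputation, coverage was 93% at 10% missing, 92% at 15%, 90–91% at 20% and 86–88% at 30%. Without arm it was 94%, 92–93%, 92% and 84–87%. At this effect size most of the loss comes from treating imputed values as observed. Rejection rates show the same: at 20% missing without a residual draw, single imputation with arm rejected in 81% of datasets, against 68–69% for complete case. That excess is false precision.

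**5. Binary outcomes.** For illustration, take the response rates in the Introduction: over 90% for B4DT and 65% for CBT, a gap of 25 points. They come from separate sources and are not a prediction for this trial.
- Equal missingness, imputation that preserves proportions: 25 × 0.85 = 21.3 points at 15% missing, 25 × 0.80 = 20 at 20%, 25 × 0.70 = 17.5 at 30%.
- Imputed scores dichotomised and all classed as responders, 25% missing in B4DT and 5% in CBT: 0.75 × 90 + 25 = 92.5 against 0.95 × 65 + 5 = 66.75, a gap of 25.75 points. There is no shrinkage.
- The same with the missing shares reversed: 0.95 × 90 + 5 = 90.5 against 0.75 × 65 + 25 = 73.75, a gap of 16.75 points.

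**The case against.** The strongest reply is that a one-clause list of inputs is not an exclusion, and that the published scripts may already include arm. This stands in part. It cannot be said that the script omits arm, only that the text, followed as written, does. Since the text states what the imputation is based on, it should be put right whatever the script contains.

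The second reply is that little depends on this analysis. It runs only above 10% missing, alongside the complete-case results, for outcomes that the plan treats as exploratory and without a margin. This is correct and limits the consequence. It does not remove it, because judging reliability is the whole purpose of the added analysis.

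A reader might also infer more than the documents support:
- *Every group difference is shrunk.* Dropout comes from attendance and economic outcomes have a separate imputation. Complete-case results are still reported, and the primary per-protocol analysis imputes nothing.
- *The NEQ is hit hardest because it has no baseline score.* The factor in step 2 does not depend on how well baseline predicts the outcome. The NEQ is exposed like the other scales, not more.
- *A harm signal would be hidden.* The semi-structured adverse-event questions go into a frequency table and serious events are described case by case.
- *Poor interval coverage is the result of leaving out arm.* Step 4 shows that much of it remains with arm included.
- *The bias always runs towards no difference.* That needs missingness at random given baseline, and step 5 shows exceptions for dichotomised outcomes. A true difference of zero is not shrunk.

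**Conclusion.** The point holds in limited form. Followed as written, the supplementary imputed analysis of the clinician-rated and self-rated secondary outcomes, including the NEQ total, shrinks a true difference by roughly the missing share. That is just over 10% at the trigger, 15% at 15% missing, 20% at 20% and 30% at 30%. Under the same assumption, neither the complete-case analysis nor imputation with arm has this bias.

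The conclusion rests on missingness at random given baseline and on the listed inputs being the full list. The size for response and remission is less certain, because it also depends on how missingness splits by arm and how imputed values are turned into a yes or no. The primary conclusion of the trial is not touched. The change is nonetheless worth making, since it is small and the present rule can only weaken the check it is meant to provide.

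**What to change.** In Statistical analysis, Secondary outcomes, state that randomised arm is in the imputation model, or that imputation is done separately by arm, for the outcomes this imputation covers. Check that the published script does the same and correct it if not.

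State also that multiple imputation or direct likelihood will be used, so that the intervals carry the imputation uncertainty. Adding arm corrects the estimate but not the coverage. For response and remission, say how imputed values lead to responder and remitter status.

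Make the same statement for the intention-to-treat sensitivity analysis of the primary outcome, where missing values are estimated by maximum likelihood and no predictors are named. If arm were left out there and B4DT were truly worse, the shrinkage would favour non-inferiority.

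The cost is a few words in two paragraphs, one term in the imputation model, and some recoding if the script currently imputes once. No new data are needed.
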